14.2 Informed consent

No participant may be admitted into this study until the investigator has obtained her legally effective informed consent. An investigator shall seek such consent only under circumstances that provide the prospective participant with sufficient opportunity to consider whether or not to participate in the study. Informed consent must be obtained without coercion, undue influence or misrepresentation of the potential benefits or risks that might be associated with participation in the study.

Informed consent encompasses all oral or written information given to the participants about the study and study materials. This includes the consent form signed by the participant, recruitment advertising and any other information provided to the participant. All such information that is given to the participant will be in a language that is understandable to her. The information will not include any language in which the participant is made to waive any of her rights or which releases or appears to release the investigator or the investigators institution.

Informed consent will be documented by the use of a written consent form that is signed by the participant (or participant's mark if she cannot sign). A copy of the signed consent form will be given to each participant. The consent form includes each of the basic elements of an informed consent document and describes each of the risks or discomforts to the participant that have been identified as reasonably foreseeable.

14.3 Participant confidentiality

The confidentiality of all participants enrolled in the study will be protected to the fullest extent possible. Study participants will not be identified by name on any document sent or in any report or publication resulting from data collected in this study.

14.4 Regulatory and ethical compliance

This clinical study was designed and shall be implemented and reported in accordance with the ICH Harmonized Tripartite Guidelines for Good Clinical Practice, with applicable local regulations and with the ethical principles laid down in the Declaration of Helsinki.

14.5 Responsibilities of the investigator and IRB

The protocol and the informed consent form have been reviewed and approved by a properly constituted Independent Ethics Committee/Research Ethics Boards (IRB) before study start. Signed and dated statements that the protocol and informed consent have been approved by the IRBs have been obtained by the investigator before study initiation.

Prior to study start, all investigators are required to sign a protocol signature page confirming his/her agreement to conduct the study in accordance with these documents and all of the instructions and procedures found in this protocol and to give access to all relevant data and records to monitors, auditors, IRBs, and regulatory authorities as required.

15.0 DISSEMINATION STRATEGIES

This indicates the steps that will be taken to ensure the project outcomes are brought to the attention of stakeholders. The findings of the study will be presented at conferences (both international and local) so as to disseminate them to a large body of professionals in the field of Obstetrics and Gynaecology. We will also publish them in high impact peer reviewed journals for wider dissemination of information. The findings will be used in counselling pregnant women with sickle cell disease at the various antenatal clinics on complications associated with the disease and preventive measures that may be employed. Charts will be created to facilitate counselling at the various antenatal clinics. We will issue press releases about the findings of the study.

7.							
8.							
9.							
10							
11							
12							
13							

Sample for Haemoglobin Fraction Taken

Yes No

Sample for Full Blood Count

Yes No

Haemoglobin Level (At Today Visit)

(g)

URINALYSIS TODAY

Leukocyte

- ± + ++

+++

Nitrite

- ± +

Urobilinogen

Negative Positive

Protein

- + + ++

+++ +++++

Random Urine Sample Sent for UPCR

Yes No

pH

Negative Positive

Specific Gravity

	Negative	Positive
Ketones		
Bilirubin		
Glucose	 -	 ±  +  ++
	 +++	 Q+++ 

ULTRASOUND

Date of Result

Ultrasound Report

Ultrasound result

Confidential

Page 6

STUDY DRUG

Patient Given Study Drug?

Yes No

Name of Clinician

APPENDIX 07 e-follow up visit*Confidential*

PIPSICKLE

Visit

Page 1

Record ID

Date of Follow-up Visit

Gestational Age at FollowUp Visit

(weeks)

(days)

FollowUp Visit Type	Scheduled	Unscheduled
---------------------	-----------	-------------

Reason for Unscheduled Follow-Up Visit	Sickle Cell Crisis
	Pregnancy Complications
	Adverse Event Report

Others

Sickle Cell Crisis

Vaso-occlusive

 Haemolytic
 Sequestration
 Acute Chest Syndrome (ACS)
 Anaemia/Haemolytic
 Others
(Specify)

Others

Pregnancy Complications

(Specify)

Other Reason for Unscheduled Followup

(please specify)

Confidential

Page 2

ADVERSE EVENTS REPORT

Is there an Adverse Event (AE)? Yes No

Adverse Event (AE) - 1

(Brief description of the nature of AE)

Start Date

(dd-mm-yyyy)

Stop Date

(dd-mm-yyyy)

Severity Mild Moderate Severe (SAE)

Category of AE	Life Threatening
	Hospitalization
	Congenital anomaly
	Required intervention to prevent permanent impairment
	Persistent Disability / Incapacity
	Other

Other (Category of AE)

Relationship of AE to Study Drug	Unrelated
	Possibly Related
	Probably Related

Definitely Related

Action Taken No action taken (i.e. further observation only) Study drug dosage adjusted/temporarily interrupted Study drug permanently discontinued due to this adverse event Concomitant medication given Non-drug therapy given Patient hospitalized/patient's hospitalization prolonged

Add Another Adverse Event (AE)? Yes No

Adverse Event (AE) - 2

(Brief description of the nature of AE)

Start Date

(dd-mm-yyyy)

Stop Date

(dd-mm-yyyy)

Confidential

Page 3

Severity	Mild	Moderate	Severe (SAE)
Category of AE	Life Threatening		
	Hospitalization		
	Congenital anomaly		
	Required intervention to prevent permanent impairment		
	Persistent Disability / Incapacity		
	Other		
Other (Category of AE)			
Relationship of AE to Study	Unrelated		
	Possibly Related		
	Probably Related		
	Definitely Related		
Action Taken	No action taken (i.e. further observation only)		
	Study drug dosage adjusted/temporarily interrupted		
	Study drug permanently discontinued due to this adverse event		
	Concomitant medication given		
	Non-drug therapy given		
	Patient hospitalized/patient's hospitalization prolonged		
Add Another Adverse Event (AE)?	Yes	No	
Adverse Event (AE) - 3			
	(Brief description of the nature of AE)		

Start Date

(dd-mm-yyyy)

Stop Date

(dd-mm-yyyy)

Severity	 Mild	 Moderate	 Severe (SAE)
----------	-------------------------------	-----------------------------------	---------------------------------------

Category of AE	 Life Threatening
	 Hospitalization
	 Congenital anomaly
	 Required intervention to prevent permanent
	 impairment
	 Persistent Disability / Incapacity
	 Other
	
	

Other (Category of AE)

Relationship of AE to Study Drug	 Unrelated
----------------------------------	------------------------------------

 Possibly Related
 Probably Related
 Definitely Related

Confidential

Page 4

Action Taken	No action taken (i.e. further observation only)
	Study drug dosage adjusted/temporarily interrupted
	Study drug permanently discontinued due to this adverse event
	Concomitant medication given
	Non-drug therapy given
	Patient hospitalized/patient's hospitalization prolonged

Any Admission since last visit?	Yes	No
---------------------------------	-----	----

if yes: Specify reason

Duration

Day(s) Week(s)

Month(s)

Have you had blood transfusion since last visit? Yes No

Date of blood transfusion?

How many units of blood?

Are you on any of the following drugs?

None

Paludrine

Hydroxyurea

Folic Acid

Penicillin V

-
-
- Multivitamin
-
- Ciklavit
-
- Astymin
-
- Jobelyn
-
- Vitamin B
-
- Vitamin C
-
- Others
-

Others

PHYSICAL EXAMINATIONS

Weight

(kg - 2 Decimal Places)

Weight

(g)

Fundal Height

(corresponding to week size)

Confidential

Page 5

BP

(Systolic)

(Diastolic)

Pulse Rate

Pulse Oximetry (SpO2)

Respiratory Rate

Temperature

LABORATORY

Haemoglobin Level (At Today Visit)

(g)

Urinalysis Today

Leukocyte

- ± + ++

+++

Nitrite

- ± +

Urobilinogen

Negative Positive

Protein

- ± + ++

+++ +++++

Random Urine Sample Sent for UPCR

Yes No

pH

Blood		Negative	Positive
			
Specific Gravity			
Ketones		Negative	Positive
			
Bilirubin		Negative	Positive
			

17-06-2020 7:50am

Powered by REDCap

Confidential

Page 6

Glucose

 - ± + ++ +++ +++++**Full Blood Count**

Date of Full Blood Count Result

PCV

(%)

Haemoglobin

(g/dl)

Total WBC

(cells/ml)

Neutrophils

(%)

Lymphocytes

(%)

Basophils

(%)

Eosinophils

Monocytes

(%)

Platelet Count

(cells/ml)

FBC Result

Is Urine M/C/S Result Available? Yes No

Urine M/C/S Result Date

Urine M/C/S Result

Haemoglobin Fraction

Date of Haemoglobin Fraction

 Hb S

 Hb F

 Hb A2

 Hb A1C

 Hb C

 Other

Hb S

Hb F

Hb A2

Hb A1C

Hb C

Hb Other

Haemoglobin Fraction Result

Date UPCR Done

UPCR Result

(Last Sample Collected)

ULTRASOUND

Date of Ultrasound Result

Ultrasound Report

Ultrasound Result

Clinical Plan

Stable continue present management

Change in clinical plan

Change in other co-medication

Additional Medication or Discontinuation

Others

Confidential

Page 8

Change in Clinical Plan

(Specify)

Change in Medication

(Specify)

Additional Medication or Discontinuation

(Specify)

Other

Referrals Made

None

Hospitalization

Blood Transfusion

Nutritional Support

- Psychosocial counseling
- Social support
- Other
-
-
-

Other

STUDY DRUG

Patient Given Study Drugs?

 Yes No

Pill Count from Last Visit

(Pill Remaining)

Study Drug Adherence (Since Last Visit)

(%)

Name of Clinician

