8.3 Reporting Adverse Events

Study site coordinators will document on the appropriate study e-CRF all AEs reported by or observed in enrolled study participants regardless of severity and presumed relationship to study product. The study clinician must provide on this form information on symptoms, time of onset, severity, frequency, product-relatedness, actions taken and participant outcome. The PI may request additional information from the site if it is needed to evaluate the AE. Site coordinators will report information on SAEs to the local Ethics committee in accordance with the local committee requirements.

All adverse events must be recorded on the e-CRF with the following information:

1. the severity grade (mild, moderate, severe)
2. its relationship to the study drug(s) (see section 8.2)
3. its duration (start and end dates or if continuing at final exam)
4. whether it constitutes a serious adverse event (SAE)

- All adverse events recorded at any time after baseline on the CRF will be summarized at analysis.

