8.4 Serious Adverse Events (SAEs)

A SAE is defined as an event which:

- is fatal or life-threatening
- results in persistent or significant disability/incapacity
- constitutes a congenital anomaly/birth defect
- requires inpatient hospitalization or prolongation of existing hospitalization, unless hospitalization is for:
 - routine treatment or monitoring of the studied indication, not associated with any deterioration in condition
 - elective or pre-planned treatment for a pre-existing condition that is unrelated to the indication under study and has not worsened since the start of study drug
 - treatment on an emergency outpatient basis for an event not fulfilling any of the definitions of a SAE given above and not resulting in hospital admission
 - social reasons and respite care in the absence of any deterioration in the patient's general condition
- is medically significant, i.e. defined as an event that jeopardizes the patient or may require medical or surgical intervention to prevent one of the outcomes listed above

Unlike routine safety assessments, SAEs are monitored continuously and have special reporting requirements.

All adverse events should be treated appropriately. Treatment may include one or more of the following:

- ❖ No action taken (i.e. further observation only);
- ❖ Study drug dosage adjusted/temporarily interrupted;
- ❖ Study drug permanently discontinued due to this adverse event;
- ❖ Concomitant medication given;
- ❖ Non-drug therapy given;
- ❖ Patient hospitalized/patient's hospitalization prolonged.

The action taken to treat the adverse event should be recorded on the adverse event section of the e-CRF.

Once an adverse event is detected, it should be followed until its resolution or until it is judged to be permanent, and assessment should be made at each visit (or more frequently, if necessary) of any changes in severity, the suspected relationship to the study drug, the interventions required to treat it, and the outcome.

Information about common side effects already known about the investigational drug will be included in the patient informed consent and should be discussed with the patient during the study as needed.

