8.5 Reporting SAEs

All SAEs should be reported to PIP-SICKLE administrative core & steering committee as soon as possible after the SAE is identified by site personnel. It is strongly recommended that site personnel report SAEs within 24 hours of the study site becoming aware of the problem. The investigator should complete ***SAE report form (Appendix xi)*** and forward to the DSMC/EMC. The investigator may report the SAE via telephone or email; however a SAE report form must be completed as soon as possible after the informal report.

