APPENDIX 11– SAE REPORT FORM

SEVERE ADVERSE EVENT (SAE) REPORT FORM

STUDY TITLE	Low dose aspirin for preventing intrauterine growth restriction and preeclampsia in sickle cell pregnancy (PIPSICKLE): a randomised controlled trial.		
Site No.			
SITE Name			
PATIENT ID		DATE OF REPORT	dd-mm-yyyy

1.	SAE Date of Onset:	dd-mm-yyyy
2.	SAE Date Stopped:	dd-mm-yyyy
3.	Location of SAE:	
4.	Was this an unexpected adverse event?	 Yes  No
5.	Brief description of participants (do not include personal identifiers):	Age
		Diagnosis for study participation
6.	Brief description of the nature of the SAE: attach description, if applicable	
7.	Category of SAE:	 Date of Death: dd-mm-yyyy  Life threatening  Congenital anomaly, birth defects  Life threatening  Required intervention to prevent impairment (permanent)  Hospitalization  Disability

		 Other:
8.	Describe study intervention	
9.	Relationship of event to intervention:	 Unrelated  Possible  Definite
10.	Was the study intervention discontinued due to the event?	 Yes  No
11.	What steps were taken to treat the SAE?	
12.	List relevant tests, lab data, history, and pre-existing medical conditions:	
13.	Report type:	 Initial  Follow-up  Final

Print Name of Site Investigator

Signature of Principal Investigator

Date

Print Name of Principal Investigator

Signature of Principal Investigator

Date

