8.2 Serious Adverse Events (SAEs)

A Serious Adverse Event (SAE) is defined as an event which:

- is fatal or life-threatening
- results in persistent or significant disability/incapacity
- constitutes a congenital anomaly/birth defect
- requires inpatient hospitalization or prolongation of existing hospitalization, unless hospitalization is for:
 - routine treatment or monitoring of the studied indication, not associated with any deterioration in condition.
 - elective or pre-planned treatment for a pre-existing condition that is unrelated to the indication under study and has not worsened since the start of study drug.
 - treatment on an emergency outpatient basis for an event not fulfilling any of the definitions of a SAE given above and not resulting in hospital admission.
 - social reasons and respite care in the absence of any deterioration in the patient's general condition.
- is medically significant, i.e., defined as an event that jeopardizes the patient or may require medical or surgical intervention to prevent one of the outcomes listed above

The number and proportion of participants who experience SAEs will be analysed and presented. The appropriate grading of severity of the SAEs will also be presented in counts and proportion. A listing of SAEs experienced will be included per participant.

If any serious adverse events occur in >5% of individuals who receive either intervention, the time to occurrence of the adverse event will be summarized using median (IQR) and graphically with Kaplan-Meier curves.

Table shell 6. Serious adverse events – summary

SAE	LDA, n(%)	Placebo, n(%)	Overall
Total			
Listed			

Table shell 7. Serious adverse events – list

record_id	SAE	Relationship	Comments including action taken

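### The follow-up e-CRF labels its top severity grade as SAE and has no seriousness item, so SAE counts are at risk of misclassification and SAE severity cannot be graded reliably

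*Protocol*

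**What the plan says.** **What must be recorded.** Protocol 8.3 lists four items for every adverse event on the e-CRF. The first is "the severity grade (mild, moderate, severe"; the fourth is "whether it constitutes a serious adverse event (SAE".

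**What an SAE is.** Protocol 8.4 defines it by outcome: death or threat to life, disability, congenital anomaly, medical significance, or an event that "requires inpatient hospitalization or prolongation of existing hospitalization, unless hospitalization is for" one of several listed exceptions. SAP 8.2 repeats this definition.

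**What the form offers.** In each of its three adverse-event slots, the follow-up e-CRF (Protocol Appendix 07) prints "Severity Mild Moderate Severe (SAE". There is no serious yes/no item. A separate field, *Category of AE*, lists outcomes such as hospitalization and "Required intervention to prevent permanent impairment", and ends in *Other*.

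**Related forms.** Under Protocol 8.5, "a SAE report form must be completed as soon as possible after the informal report". That form (Appendix 11) and the end-of-study e-CRF (Appendix 09) both expand SAE as severe rather than serious. On the SAE form, the item "Relationship of event to intervention" has three levels, against four in Protocol 8.2 and on the follow-up e-CRF; the probable level is missing.

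**What will be reported.** SAP 8.2 plans the number and proportion of participants with SAEs and adds: "The appropriate grading of severity of the SAEs will also be presented in counts and proportion". It does not say which field identifies an SAE.

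**The concern.** Severity is how intense an event is; seriousness is what it led to. One box is labelled as if the two were the same. A moderate event that leads to admission is serious under Protocol 8.4, yet its severity box does not say SAE. A severe event that meets no 8.4 criterion is labelled SAE. Protocol 7.7 itself names events of the second kind that need not be serious, such as severe nausea or severe pruritus.

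The SAE proportion by arm is a main safety output. Recognition of an SAE also starts the reporting to the monitoring committee (Protocol 8.5) and is the condition for considering unblinding (Protocol 3.6.2). Because three forms share the confusion, staff who read SAE as severe may never open the SAE form for a moderate event with admission.

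**Working it through.** The plan gives no figure for this point, so there is none to reproduce. The check sets the fields side by side and then follows each way of using the box.

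**1. Where each required piece can come from**

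| Needed | Follow-up e-CRF | SAE report form |
|---|---|---|
| Severity grade | Yes, but the top level is labelled SAE | No severity item |
| Serious yes/no | No item | Implied by filing the form |
| Death | Not in *Category of AE* | Yes, as a date |
| Admission | *Category of AE*, *Action Taken*, and an item on admission since the last visit, with reason | Yes |
| Relatedness | Four levels | Three levels |

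The severity box is therefore the only source for the SAE severity grading in SAP 8.2.

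**2. The box cannot do both jobs.** Let *a* = severe and serious, *b* = severe but not serious, *c* = serious but not severe.

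- *Box ticked as an SAE flag.* Counted SAEs = a + c, which is the true number. Every one of them reads as severe, so the grading is 100% severe by construction, and the events in *b* cannot be graded severe without being called SAEs.
- *Box ticked on intensity.* The grading is usable, but the box no longer identifies SAEs. If it were nevertheless the only SAE source, counted = a + b and true = a + c, so

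 error = (a + b) − (a + c) = b − c.

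The error can be positive, negative or zero. The share of true SAEs left unflagged would be c / (a + c). The documents give no rates for *b* or *c*, so that share can lie anywhere from 0% to 100%.

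**3. Sensitivity of one planned rule.** SAP 8.2 adds a time-to-event summary when an SAE occurs in more than 5% of those who receive either intervention. Read per arm, with about 238 women (Protocol 3.2):

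- 0.05 × 238 = 11.9
- 11/238 = 4.62% (not triggered)
- 12/238 = 5.04% (triggered)

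Near that boundary, one reclassified participant switches the summary on or off.

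**4. How good the fallback fields are.** *Category of AE* has no option for not serious and none for death. *Other* could mean medically significant or not serious. *Hospitalization* does not separate the admissions that Protocol 8.4 excludes, although the reason field for admissions may help. The SAE form exists only where staff recognised an SAE. These fields recover most SAEs, but not with certainty.

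**The case against.** The strongest reply is that no document makes the severity box the source of the SAE count. SAP 8.2 uses the outcome definition, and the outcomes are collected: *Category of AE* and *Action Taken* in every slot, admissions since the last visit, a dedicated SAE form that includes death, and an SAE outcome item at end of study. This stands, and it rules out several stronger readings that a reader might infer.

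- *That SAE counts will be wrong.* The documents do not show this. Counts built from the other fields can be largely right.
- *That a moderate event with admission cannot be recorded as serious.* As printed, Moderate can be combined with the category *Hospitalization*, and the SAE form has no severity item to conflict with it. The printout does not show whether the category field is branched or may be left blank.
- *That a fixed share is lost.* Supposing that half of admitted events are graded below severe, and concluding that half go unflagged, only returns the assumption. It also presumes that the box is the sole source.
- *That the comparison between arms is biased.* The form is common to both arms and Protocol 3.6.2 keeps site staff blinded. Nothing points to a difference by arm.
- *That a planned SAE severity table is lost.* SAP 8.2 has one sentence; Table shells 6 and 7 have no place for severity.

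The reply does not remove the defect. The form omits an item that Protocol 8.3 requires, the SAP names no SAE source, and no other field supplies severity. The relatedness mismatch is minor, since the e-CRF carries all four levels. Even so, the relationship column of SAP Table shell 7 could be filled from two sources that disagree.

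**Conclusion.** The concern holds as a recording defect with a defined consequence. The severity item contradicts Protocol 8.3 and does not fit the outcome definition in Protocol 8.4 and SAP 8.2.

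- **SAE counts:** at risk of misclassification, of unknown size and direction, unless derived from category, action, admission and SAE-form data. If the box alone were used and ticked on intensity, the error would be b − c. That condition is an assumption, not something the documents state.
- **SAE severity grading:** either one level by construction, or usable only if the box plays no part in identifying SAEs. This follows from the forms alone, because no other severity source is printed.
- **Relatedness:** three levels on one form and four on the other; minor, but to be reconciled.

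The item is wrong as written and should be corrected. It does not by itself show that the safety comparison is invalid.

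**What to change.** 1. In each of the three adverse-event slots, replace the item with two: severity (mild, moderate, severe) and serious (yes/no), the latter with the Protocol 8.4 criteria including death.
2. Change severe to serious in the SAE wording of the end-of-study e-CRF and the SAE report form.
3. Use the four relatedness levels of Protocol 8.2 on both forms.
4. State in SAP 8.2 that an SAE is identified by the 8.4 criteria from the category, action, admission and SAE-form data, and not by the severity box.
5. For records already entered, re-derive seriousness blinded to arm before database lock, and report that SAE severity taken from the old field is unreliable.

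The cost is a few form edits and a one-off blinded review of entered events. The follow-up e-CRF printout carries a June 2020 stamp, the protocol is Version 4 of May 2024, and SAP 6.4 describes compliance assessment in the past tense. Much of the data may therefore already be in, in which case steps 4 and 5 matter most.
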